10.3 Study Monitoring

Study monitoring is undertaken to ensure that the rights and well-being of study infants are protected, that the reported study data are accurate, complete, and verifiable, and that the conduct of the study is in compliance with the currently approved protocol, with International Conference on Harmonisation Good Clinical Practice (ICH GCP), and with applicable regulatory requirement(s).

The Sponsor's monitoring frequency has been determined by an initial risk assessment performed prior to the start of the study. A detailed Clinical Monitoring Plan (CMP) has been developed detailing the frequency and scope of the monitoring for the study. Throughout the conduct of the study, the risk assessment will be reviewed, and the monitoring frequency adjusted, as necessary.

Remote and central monitoring will be conducted for all participating sites. The scope and frequency of monitoring has been determined by the risk assessment and detailed in the Clinical Monitoring Plan (CMP) for the study. Unresolved or significant findings from remote monitoring visits may result in the escalation from remote visits to on-site visits.

- Regular remote and central monitoring will be performed according to the study specific Clinical Monitoring Plan (CMP).
- Central monitoring will occur regularly focusing on targeted source data verification of scheduled study assessments.
- Remote monitoring will occur every 6 months focusing on site compliance with ICH-GCP, informed consent and recruitment processes and essential document management.
- Data will be evaluated for compliance with the protocol requirements and accuracy in relation to source documents as defined in the CMP.
- Following written standard operating procedures, the monitors will verify that the clinical study is conducted, and data are generated, documented, and reported in compliance with the protocol, GCP and the applicable regulatory requirements.

- Each participating site will be provided with copies of monitoring reports within 7 days of each remote monitoring visit.
- Independent audits may be conducted by the Sponsor or a representative of the Sponsor, to ensure monitoring practices are performed consistently across all participating sites and that monitors are following the CMP.

11 STATISTICAL METHODS

11.1 Sample Size Estimation

The sample size for BLUEPRINT is designed to address the robustness of early respiratory phenotypes identified predicting BPD. The prevalence of survival with BPD within the ANZNN is 0.69. Based on the R package *pmsampsize* version 1.1.3 described by Riley et al in “*Calculating the sample size required for developing a clinical prediction model*”,⁽³⁶⁾ we estimated that the following sample size will be required to develop a clinical risk prediction model with BPD (yes/no) as the outcome: assuming a BPD prevalence of 0.69 (69%; all grades) and a moderate C-index of 0.75 is achievable (latest estimates from PRELIM manuscript support this) with a binary logistic regression prediction model with BPD (yes/no) as the outcome, a minimum sample size of 500, 550 and 600 infants was estimated based on 10, 11 or 12 predictor variables respectively (from any domain of clinical, imaging and protein data). We estimate that the predictive model developed in BLUEPRINT may have up to 10-12 predictor variables which is partly based on the latest PRELIM manuscript where several basic clinical covariates (e.g. gender, gestational age) and only single proteins were included (given the limited sample size in PRELIM), however there were multiple proteins that were significantly correlated with BPD and there will be additional clinical covariates and other model terms (interactions, non-linear terms, which are counted as additional predictor variables terms in the *pmsampsize* sample size estimation) that will likely be critical to include in the BLUEPRINT study in order to achieve high performing predictive models.

The calculation above derived from the *pmsampsize* R package considers multiple criteria to arrive at an appropriate sample size that ensures precise predictions, minimises prediction errors and model overfitting/optimism, and allows for sufficient stratification by factors known to exert a strong signal on neonatal outcomes (e.g. gestational age/weight, sex and intubation in first 10 days).

This sample size prediction assumes the distribution of births within the 22-25+6-, 26-28+6- and 29-31+6-week GA cohorts as reported in the ANZNN. Between 2018-2020, approximately 750 infants aged 22-32 weeks' gestation were born per annum in Victoria who would have met the projects eligibility criteria; 37% <28 weeks' GA, overall mortality 7% (Data Safer Care Victoria). To achieve the desired sample size a recruitment rate of 20-25% of all eligible births (approximately 2250 births) would be required. Assuming a 5% loss to follow up/withdrawal rate between the first week after birth and BPD assessment a sample size of 550 infants included into the primary aim of the study (early life respiratory phenotype description) would allow 525 infants for inclusion in the BPD prediction modelling data set. This should also allow for approximately 400-450 surviving infants available for 2-year follow up (assuming >80% retainment rate after discharge).

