2 INTRODUCTION AND BACKGROUND

2.1 Background and rationale

Globally, 15 million babies are born preterm each year, and 1 million die.(1) Respiratory disease is the greatest cause of illness for these infants;(2) almost 75% born before 32 weeks' gestation receive assisted respiratory support. However, surviving to discharge home is not the endpoint for this respiratory burden. Ventilation of the underdeveloped lung is a double-edged sword; necessary for survival but risk long-term injury to the lungs.(2) Despite 40 years of advances in respiratory support, many preterm infants develop early lung injury that eventually leads to chronic lung disease (CLD) throughout infancy, childhood and in adult life. This burden is increasing.(3, 4)

The accepted measure of in-hospital respiratory morbidity, bronchopulmonary dysplasia (BPD) diagnosed at 36 weeks' postmenstrual age (PMA)(5), does not reliably predict respiratory complications in later life and has often been conflated to represent CLD status.(6) Irrespective of BPD status, childhood respiratory function in preterm survivors is now worse than 25 years ago. Abnormal childhood respiratory function is associated with adult obstructive CLD and deteriorating lung function.(7, 8) Necessitating urgent re-evaluation of how early preterm respiratory disease is defined, identified and managed, in order to reduce the ensuing burden on infants, families and health services.

Avoiding the trajectory towards CLD in later life requires modulation of the early life events that initiate the lung injury/inflammation cascade at and shortly after birth (**Figure 2a**). Currently, these events are defined from crude measures that poorly categorise the complexity of prematurity and NICU management. To provide the right lung protective treatment, at the right time, clinicians need precise guidance to make decisions that avoid or modify the initial disease process.

This study aims to bring together the tertiary-level NICUs in Victoria to:

1. Define early-life respiratory phenotypes in preterm infants,
2. Link these phenotypes to medium (in-hospital) and long-term respiratory outcomes, specifically BPD and respiratory health at 1 and 2 years of corrected age, and
3. Integrate protein biomarkers, lung imaging and clinical tools to define the continuum of modifiable mechanical-molecular-clinical interactions occurring in early preterm life.

[figure not shown]

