4.3.2 Inclusion Criteria

Each infant must meet all inclusion criteria to be eligible for enrolment on this study:

1. Born between 22+0 and 31+6 weeks' gestation.
2. Birth admission in a participating perinatal Victorian NICU.
3. The infant has a parent/legal representative capable of understanding the informed consent document and providing consent on the infant's behalf AND consent is obtained antenatally or within 72 hours from birth.

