BPD status during 36 weeks' PMA will be assessed using the Modified Walsh definition and standard oxygen reduction test (ORT), and Jensen criteria for Grading from no BPD, mild, moderate and severe (Grade 0-3) (5, 10). Death before 36 weeks' PMA due to a primary respiratory cause will be coded as severe BPD using the 2018 NICHD Grade 3A BPD definition; *'early death between 14 days postnatal age and 36 weeks' PMA from persistent parenchymal lung disease and respiratory failure that is not attributable to other neonatal morbidities'*. Inclusion of death due to non-respiratory causes may result in misclassification in the prediction models. The primary and critical contributors to all deaths before 36 weeks' PMA will be documented to allow secondary analysis for 'all cause' mortality in the prediction models. The 36-week BPD Assessment should occur on the date determined to be 36+0 to 36+6 weeks PMA.

If the BPD assessment is completed outside of the 36+0 to 36+6 weeks' PMA assessment window, as the infant was discharged home from hospital early self-ventilating in air (SVIA) before 36+0 weeks PMA, then these infants will be coded as not having BPD. Should the condition of the infant change within the 36-weeks PMA (e.g. they are re-admitted to any hospital between discharge home and 36+6 weeks PMA), then the participating site must update the 36-Week PMA BPD Assessment CRF, if applicable.

Lung imaging will be repeated as per Section 6.2.4, and the appropriateness of studying the infant will be re-affirmed with the clinical staff. For scheduled weekly or pre-discharge measures, consent will also be re-affirmed with the parents/legal representative and documented in the participant's medical record as per the Manual of Operating Procedures.

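### The planning BPD prevalence of 0.69 is applied to the whole 22+0 to 31+6 week cohort but is not credible against the protocol's own figures for that cohort

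*Protocol*

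**What the plan says.** Protocol section 11.1 opens the sample size with "The prevalence of survival with BPD within the ANZNN is 0.69". The next sentence uses the same number under another name: "assuming a BPD prevalence of 0.69 (69%; all grades) and a moderate C-index of 0.75 is achievable". The result is "a minimum sample size of 500, 550 and 600 infants was estimated based on 10, 11 or 12 predictor variables respectively". No years, denominator or gestation range are given for 0.69. The following paragraph says that the calculation assumes the ANZNN mix across three gestation bands running from 22 to 31+6 weeks. That matches inclusion criterion 1 in section 4.3.2, "Born between 22+0 and 31+6 weeks' gestation", so the figure is presented as valid for every eligible infant.

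Four other statements bear on it:

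- Section 11.1 describes about 750 eligible Victorian births a year, with "37% <28 weeks' GA, overall mortality 7" per cent.
- Section 2.1 says that "almost 75% born before 32 weeks' gestation receive assisted respiratory support".
- Section 2.1 also says that BPD is currently defined by respiratory support and oxygen dependency at 36 weeks' postmenstrual age.
- Section 6.2.7 sets the coding. For infants who go home in air before 36+0 weeks, "then these infants will be coded as not having BPD". Deaths before 36 weeks from a primary respiratory cause are coded as severe BPD.

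**The concern.** BPD at 36 weeks can only arise among infants who needed support and survived, plus the respiratory deaths that section 6.2.7 adds. When the protocol's figures for support, mortality and gestation are put together, 0.69 leaves almost no room for supported infants who recover before 36 weeks. It also needs BPD in at least half of the more mature majority.

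The text moves from survival with BPD to BPD prevalence as if they were the same quantity. They are not: the modelled outcome in section 6.2.7 includes some infants who died, and the two may have different denominators.

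The prevalence feeds directly into the required sample size, into the number of model parameters the data can carry, and into the expected BPD and non-BPD counts for the prediction, proteomic and Day 14/28 imaging comparisons.

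**Working it through.** **1. Reproducing the stated sizes.** Inputs from section 11.1: prevalence 0.69, C-index 0.75, and 10, 11 or 12 parameters. Assumed, because the protocol does not state them: target shrinkage S = 0.9, optimism of 0.05 in the scaled R², and a margin of 0.05 on overall risk. Converting C = 0.75 to a Cox-Snell R² with a normally distributed linear predictor gives R² = 0.162. The shrinkage criterion is the binding one:

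n = P / [(S − 1) × ln(1 − R²/S)]

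This is about 50.25 infants per parameter, so 503, 553 and 603 for P = 10, 11 and 12, against the stated 500, 550 and 600. The protocol's arithmetic is right for its inputs.

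**2. Check against support and mortality.** Inputs: 0.75 ever supported (section 2.1) and 0.07 mortality (section 11.1).

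| Reading of 0.69 | Calculation | Share of ever-supported survivors who need BPD |
|---|---|---|
| Share of births; all deaths among supported infants | 0.69 / (0.75 − 0.07) = 0.69 / 0.68 | 101.5% |
| Share of births; equal mortality in supported and unsupported infants | 0.69 / (0.75 × 0.93) = 0.69 / 0.6975 | 98.9% |
| Share of survivors; equal mortality | 0.69 / 0.75 | 92.0% |
| Share of births; all 7% of deaths among supported infants and all coded as BPD (upper bound for the 6.2.7 rule) | (0.69 − 0.07) / 0.68 | 91.2% |

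**3. Check against gestation, which does not use the 75%.** Eligible births are 37% below 28 weeks and 1 − 0.37 = 63% at 28 weeks or later. Suppose every infant below 28 weeks had BPD. Then the later group needs (0.69 − 0.37) / 0.63 = 0.508, or 51%. If 0.69 is survival with BPD as a share of births and mortality is equal across gestation, the share among survivors is 0.69 / 0.93 = 0.742, and the later group needs (0.742 − 0.37) / 0.63 = 0.59, or 59%. Any infant below 28 weeks without BPD raises these figures.

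**4. Effect of a different prevalence.** The documents give no alternative value, so the values below other than 0.69 are assumptions, with C = 0.75 throughout. The parameter count is 525 divided by the infants needed per parameter, rounded down.

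| Prevalence | N for 10 / 11 / 12 parameters | BPD / non-BPD among 525 | Parameters 525 supports |
|---|---|---|---|
| 0.69 (stated) | 503 / 553 / 603 | 362 / 163 | 10 |
| 0.50 | 435 / 478 / 522 | about 262 / 262 | 12 |
| 0.40 | 452 / 497 / 542 | 210 / 315 | 11 |
| 0.31 | 503 / 553 / 603 | 163 / 362 | 10 |
| 0.25 | 569 / 626 / 683 | 131 / 394 | 9 |
| 0.20 | 661 / 727 / 794 | 105 / 420 | 7 |

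The calculation is symmetric about 0.5, which is why 0.31 and 0.69 agree. Converting the C-index by simulation instead moves the results by a few infants (for 10 parameters, 500 to 505 at 0.69 and 564 to 571 at 0.25).

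**The case against.** A reader might infer that 0.69 is impossible and that every supported survivor would need BPD. The documents do not support that. The one reading above 100% needs all births as the denominator, all deaths among supported infants, and no respiratory deaths counted as BPD, and it then exceeds the limit by only 1.5 percentage points. It also carries over a rounded figure (almost 75%) from a background paragraph that is not tied to ANZNN or Victoria, whereas the 7% is Victorian data. The share ever supported may differ among infants admitted to these units. All of this stands, and it reduces the claim from impossible to not credible.

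A reader might also guess that 0.69 belongs to a more immature group, or is really the proportion without BPD. Nothing in the protocol shows its origin, and no BPD rate by gestation is given against which to test the 51%. No replacement value can be derived from the documents.

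Nor do they support saying that every BPD comparison would have far fewer cases than planned, or that the study is too small. A two-group comparison is limited mainly by its smaller group, which is 163 (non-BPD) at 0.69 and 163 (BPD) at 0.31. A material shortfall for 10 parameters needs a prevalence well below 0.31, for which there is no evidence here.

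What the objection does not remove is that each reading in the working still needs at least about 91% of ever-supported survivors to have BPD, and the gestation check needs at least 51% at 28 weeks or later without using the background figure at all.

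**Conclusion.** The concern holds as a defect in a planning input. Section 11.1 presents 0.69 as valid for all infants of 22+0 to 31+6 weeks, and it does not fit the protocol's own description of that population: about 91% to just over 100% of ever-supported survivors, and at least 51% of those born at 28 weeks or later, would need BPD. The first range assumes that the background support figure applies roughly to this cohort. The second rests only on the gestation split and the most lenient assumption below 28 weeks. The move from survival with BPD to BPD prevalence is a separate ambiguity that needs resolving whatever the right number is.

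The direction of the effect is unknown. Across an assumed 0.20 to 0.50, the 525 analysed infants support between 7 and 12 parameters, against 10 at 0.69. The synopsis statement that 550 infants allow up to 12 variables after 5% loss is not met even at 0.69. That is a different matter and adds no weight to this one.

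**What to change.** In section 11.1, replace 0.69 with the registry BPD proportion for infants who meet section 4.3. Build it from the three gestation bands already named there, weighted by the expected mix, and apply the section 6.2.7 coding for both early discharge in air and respiratory death before 36 weeks. State the source, years, denominator and gestation range, and use one term for the outcome throughout.

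Re-run the calculation at that value. Show a sensitivity range, for example 0.20 to 0.69, since the requirement falls and then rises across it. Restate the expected BPD and non-BPD counts and the number of candidate parameters that the 525 analysed infants support, and carry the result into the synopsis.

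The cost is one registry tabulation and revised text in two places. The stated model size may become less favourable. No extra infants and no change to study procedures are needed.

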Development of a biomarker-based BPD risk (and 1 and 2 year) prediction model: We will develop a risk prediction model for BPD diagnosed at 36 weeks, based on a combination of proteins, imaging and clinical measures (minimum 7 inputs) derived within the first 7 days after birth. Model development will include several steps starting with methods for variable selection and model fitting to testing the performance and validation of models. To test measures originally significantly associated with BPD, and identify other measures that are predictive of BPD, binary logistic regression, multiple forward stepwise logistic regression, and other classification models will be evaluated with likely measures as covariates. This approach is similar to other recent studies that developed prognostic, biomarker-based models for predicting adverse outcomes in adults with respiratory problems. (34) Model performance and discrimination will then be evaluated. Internal validation with both cross-validation and bootstrapping methods to adjust for model over-optimism and bias towards inherent overestimated performance metrics will be applied. A similar strategy will be used for developing and testing risk prediction models at 1 and 2 years, which will include initial variable selection and subsequent model performance (AUC, discrimination) and validation (cross-validation) tests. We will examine several methods (e.g. growth curve trajectory) for coding repeatedly measured predictor variables that best capture developmental changes related to lung injury over time and subsequent respiratory risks. Cox proportional-hazards regression models and Kaplan-Meier survival curves will be used to further investigate and illustrate differences in BPD risk outcomes between high-risk and low-risk groups based on prognostic scores derived from BPD risk models, which will be useful to account for infants that may be lost to follow-up before 2 years.

Testing and developing alternative machine learning models of BPD risk.

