While binary logistic regression is commonly used for developing risk prediction models when disease outcomes are binary yes/no, it will be important to test alternative risk prediction models that may be better able to handle high dimensional data (protein data, imaging data) and capture nonlinear relationships between variables. Some studies have shown a slight improvement in model prediction performance between logistic regression (LR) and machine learning (ML) algorithms,(37) while others have not.(38) AI methods are showing particular promise for providing advancements in areas where disease prediction is based on complex data such as lung imaging(39) or protein data.(40) Given BLUEPRINT will test whether integration of traditional BPD risk factors with protein, imaging and other data may improve prediction of BPD outcomes, it will be important to test alternative risk prediction models. We will test several commonly used ML algorithms (e.g. K-nearest neighbour, random forests, support vector machine). LR and ML models will all be internally validated and compared using the same data. Model performance will be compared with accuracy, sensitivity and specificity.

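### The sample size counts the 10-12 terms of the finished BPD model, but the shrinkage criterion behind it applies to every candidate parameter examined, and 525 infants support only about 10 of those

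*Protocol*

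**What the plan says.** Section 11.1 applies pmsampsize, "assuming a BPD prevalence of 0.69 (69%; all grades) and a moderate C-index of 0.75 is achievable", and reports "a minimum sample size of 500, 550 and 600 infants was estimated based on 10, 11 or 12 predictor variables respectively". The predictor count is described as a property of the model that will result: "We estimate that the predictive model developed in BLUEPRINT may have up to 10-12 predictor variables". Some extra terms are included ("interactions, non-linear terms, which are counted as additional predictor variables terms"), but candidates that are examined and then discarded are not mentioned. The calculation is credited with giving a size that "minimises prediction errors and model overfitting/optimism". After 5% loss, 550 enrolled infants are taken to leave 525 for BPD modelling.

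Section 11.2 sets out the order of work: "Model development will include several steps starting with methods for variable selection and model fitting to testing the performance and validation of models". It starts from measures already associated with BPD, also looks for others, and states that "multiple forward stepwise logistic regression, and other classification models will be evaluated with likely measures as covariates". Internal validation by cross-validation and bootstrap is planned to correct for optimism. For logistic regression against machine learning, "Model performance will be compared with accuracy, sensitivity and specificity".

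The source data are wide. Section 2.1 describes the proteomic method as untargeted, plasma is sampled at 72 hours and day 7, and section 11.2 itself calls the protein and imaging data high dimensional.

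**The concern.** Overfitting is driven by how many parameters are compared with the outcome, not by how many remain at the end. A 12-term model picked from 100 candidates has used the data far more heavily than a 12-term model fixed in advance, although both look the same in the final table. Section 11.1 sizes the second kind of model and section 11.2 describes something closer to the first.

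This matters because the BPD model sets N = 550 and is meant as a tool for everyday practice (secondary objective 3). If shrinkage falls well below 0.90, predicted risks will be too extreme in new infants: too high for high-risk infants and too low for low-risk infants. Accuracy, sensitivity and specificity do not measure that error; a calibration slope does.

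**Working it through.** **Inputs.** From section 11.1: prevalence 0.69, C-index 0.75, P = 10, 11 or 12, analysed n = 525. Assumed: target shrinkage S = 0.90, which the protocol does not state. It is used because it reproduces the stated sizes.

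**Step 1: explained variation.** A C-index of 0.75 with a binormal linear predictor means a group difference of √2 × z(0.75) = √2 × 0.6745 = 0.954. At prevalence 0.69 this gives a Cox-Snell R² of 0.1624 (maximum 0.710).

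**Step 2: reproduce the stated sizes.** The shrinkage criterion is N = P / [(S − 1) × ln(1 − R²/S)]. With S = 0.90, ln(1 − 0.1624/0.90) = −0.1990, so N = P / 0.01990, about 50.25 infants per parameter.

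| P | N computed | N stated |
|---|---|---|
| 10 | 503 | 500 |
| 11 | 553 | 550 |
| 12 | 603 | 600 |

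The other two criteria need fewer infants: 253 to 304 for the 0.05 limit on optimism in Nagelkerke R², and (1.96/0.05)² × 0.69 × 0.31 = 329 for overall risk. Shrinkage therefore governs the sample size.

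**Step 3: what 525 infants support.** 525 / 50.25 = 10.4, so about 10 parameters.

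**Step 4: count all candidates.** P is not in the documents, so a range is shown. The last column solves (1 − S) × [−ln(1 − 0.1624/S)] = P/525.

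| Candidate parameters | N needed for S = 0.90 | Expected S at n = 525 |
|---|---|---|
| 10 | 503 | 0.90 |
| 12 | 603 | 0.89 |
| 20 | 1,005 | 0.83 |
| 30 | 1,508 | 0.76 |
| 50 | 2,513 | 0.66 |
| 100 | 5,025 | 0.51 |

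R² is held at 0.1624 throughout, so the extra candidates are taken to add no explained variation.

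**Step 5: does validation show it?** Simulation at n = 525: 12 real predictors with joint true C 0.75, four clinical terms forced in, forward selection to 12 terms, independent candidates, 10-fold cross-validation, 40 replicates per setting (100 for the fixed model).

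| Candidates | Calibration slope | C in new infants | Cross-validated C, selection outside folds | Cross-validated C, selection inside folds |
|---|---|---|---|---|
| 12 (fixed) | 0.88 | 0.74 | 0.73 | 0.73 |
| 50 | 0.70 | 0.71 | 0.74 | 0.70 |
| 100 | 0.58 | 0.69 | 0.75 | 0.69 |
| 300 | 0.50 | 0.67 | 0.76 | 0.66 |
| 500 | 0.44 | 0.66 | 0.77 | 0.66 |

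With selection outside the folds, the estimate rises as true performance falls. With selection inside, it stays within about 0.02 of true performance. The effect pattern is assumed, so these figures show direction and order of size only.

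**The case against.** The strongest defence is that the protocol may not intend a screen of the whole proteome. Section 11.2 refers to measures originally associated with BPD, and section 11.1 says that several proteins correlated with BPD in the pilot. A short pilot-derived list is a natural reading and would bring P close to 10-12. The synopsis also speaks of models built on endotypes from latent class analysis, which could be formed without using BPD status. Forward stepwise regression is one of several methods to be evaluated. This stands as far as it goes: no candidate number can be read from the document. It does not settle the matter, because section 11.2 also sets out to find other predictive measures and puts no limit on the search.

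Second, optimism correction is planned, and the order of steps in section 11.2 does not say that selection stays outside the resampling. That is correct, and the detail may be in the SAP. Resampling done properly shows overfitting, however; it does not restore the shrinkage that section 11.1 relies on.

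A reader might infer more than the documents support:
- That overfitting will be severe. With 20 candidates it is modest (0.83 against 0.90).
- That the listed metrics conceal the problem, for example because calling every infant BPD gives 69% accuracy. That rule has 0% specificity, and specificity is one of the listed metrics. Section 11.2 also evaluates discrimination.
- That the selected model would do worse than clinical variables alone. In further simulations this depended on how much real signal the non-clinical markers were given. It appeared when most candidates were noise. With real signal present it occurred in one of nine settings, by 0.01.

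**Conclusion.** The point holds as a mismatch between sections 11.1 and 11.2. The stated sizes are reproduced, but they secure shrinkage of about 0.90 only for about 10 candidate parameters fixed in advance. At n = 525 the expected value is about 0.83 with 20 candidates, 0.66 with 50 and 0.51 with 100. These figures assume a 0.90 target, C = 0.75, prevalence 0.69 and no added explained variation from further candidates; the actual candidate number is unknown. Whether reported discrimination would be inflated depends on whether selection is repeated in each resample, which is left open. No calibration measure is named, although a calibration quantity sets the sample size. This should be fixed before the analysis plan is final. It does not call recruitment or data collection into question.

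**What to change.** 1. In section 11.1, state that the predictor count means candidate parameters, including interactions and non-linear terms, and that 525 analysed infants support about 10.
2. In section 11.2, limit candidates to that number by a list fixed from the pilot or by data reduction that does not use BPD status. Otherwise, replace forward stepwise selection with penalised regression and say that the 0.90 shrinkage no longer follows from the calculation.
3. State that all selection and tuning are repeated inside each bootstrap sample or fold.
4. Compare logistic and machine-learning models on optimism-corrected C-index and calibration slope, with sensitivity and specificity at a stated threshold.

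The cost is wording and computing time, with no extra infants. The downside is that reported performance may be lower and fewer single proteins may be named.
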